**Table 5 Visit Windows for PD samples (free C2, total C2 and CH50) during IVMP**

IVIg Dosing Frequency	Protocol Scheduled Visit	Scheduled Visit Day (Relative Day during the IMVP)	Protocol Window (days)	Timepoint	Window for sample**
Q2 Weeks	IMV1	1	NA	Pre-dose	Assessment date/time on or before first IVIg administration during IVMP
Q3 Weeks	IMV1	1	NA	Pre-dose	Assessment date/time on or before first IVIg administration during IVMP
Q4 Weeks	IMV1	1	NA	Pre-dose	Assessment date/time on or before first IVIg administration during IVMP
Q5 Weeks	IMV1	1	NA	Pre-dose	Assessment date/time on or before first IVIg administration during IVMP
Q2 Weeks	IMV2	15	±3	Pre-dose	Date of previous IVIg administration + 14 days ± 3 days and performed on or before IVIg administration at this visit
Q3 Weeks	IMV2	22	±3	Pre-dose	Date of previous IVIg administration + 21 days ± 3 days and performed on or before IVIg administration at this visit
Q4 Weeks	IMV2	29	±3	Pre-dose	Date of previous IVIg administration + 28 days ± 3 days and performed on or before IVIg administration at this visit
Q5 Weeks	IMV2	36	±3	Pre-dose	Date of previous IVIg administration + 35 days ± 3 days and performed on or before IVIg administration at this visit
Q2 Weeks	IMV3	29	±3	Pre-dose	Date of previous IVIg administration + 14 days ± 3 days and performed on or

					before IVIg administration at this visit
Q3 Weeks	IMV3	43	±3	Pre-dose	Date of previous IVIg administration + 21 days ± 3 days and performed on or before IVIg administration at this visit
Q4 Weeks	IMV3	57	±3	Pre-dose	Date of previous IVIg administration + 28 days ± 3 days and performed on or before IVIg administration at this visit
Q5 Weeks	IMV3	71	±3	Pre-dose	Date of previous IVIg administration + 35 days ± 3 days and performed on or before IVIg administration at this visit

**Table 6** Visit Windows for PK during DBTP and Safety FU period

[illegible]

				[REDACTED]
[REDACTED]	[REDACTED]	[REDACTED]	[REDACTED]	[REDACTED]
			[REDACTED]	[REDACTED]
[REDACTED]	[REDACTED]	[REDACTED]	[REDACTED]	[REDACTED]
			[REDACTED]	[REDACTED]
[REDACTED]	[REDACTED]	[REDACTED]	[REDACTED]	[REDACTED]
			[REDACTED]	[REDACTED]
[REDACTED]	[REDACTED]	[REDACTED]	[REDACTED]	[REDACTED]
			[REDACTED]	[REDACTED]
[REDACTED]	[REDACTED]	[REDACTED]	[REDACTED]	[REDACTED]
			[REDACTED]	[REDACTED]
[REDACTED]	[REDACTED]	[REDACTED]	[REDACTED]	[REDACTED]
		[REDACTED]	[REDACTED]	[REDACTED]

[illegible]

				[REDACTED] [REDACTED] [REDACTED]
[REDACTED]	[REDACTED]	[REDACTED]		[REDACTED] [REDACTED] [REDACTED] [REDACTED] [REDACTED] [REDACTED] [REDACTED] [REDACTED] [REDACTED] [REDACTED]
[REDACTED]	[REDACTED] [REDACTED]	[REDACTED]		[REDACTED] [REDACTED] [REDACTED] [REDACTED]
[REDACTED]	[REDACTED] [REDACTED]	[REDACTED]		[REDACTED] [REDACTED] [REDACTED] [REDACTED]
[REDACTED]	[REDACTED] [REDACTED]	[REDACTED]		[REDACTED] [REDACTED] [REDACTED] [REDACTED]
[REDACTED]	[REDACTED] [REDACTED]	[REDACTED]		[REDACTED] [REDACTED] [REDACTED] [REDACTED]
[REDACTED]	[REDACTED] [REDACTED]	[REDACTED]		[REDACTED] [REDACTED] [REDACTED] [REDACTED]
[REDACTED] [REDACTED]	[REDACTED] [REDACTED]	[REDACTED]		[REDACTED] [REDACTED] [REDACTED] [REDACTED]

1			
2			

**Table 7** Visit Windows for PD samples (free C2, total C2 and CH50) during DBTP and Safety Follow-up period

[illegible]

[REDACTED]	[REDACTED]	[REDACTED]	[REDACTED]	[REDACTED]
			[REDACTED]	[REDACTED]
[REDACTED]	[REDACTED]	[REDACTED]	[REDACTED]	[REDACTED]
			[REDACTED]	[REDACTED]
[REDACTED]	[REDACTED]	[REDACTED]	[REDACTED]	[REDACTED]
			[REDACTED]	[REDACTED]
[REDACTED]	[REDACTED]	[REDACTED]	[REDACTED]	[REDACTED]
			[REDACTED]	[REDACTED]
[REDACTED]	[REDACTED]	[REDACTED]	[REDACTED]	[REDACTED]
			[REDACTED]	[REDACTED]
[REDACTED]	[REDACTED]	[REDACTED]	[REDACTED]	[REDACTED]
			[REDACTED]	[REDACTED]
[REDACTED]	[REDACTED]	[REDACTED]	[REDACTED]	[REDACTED]
			[REDACTED]	[REDACTED]
[REDACTED]	[REDACTED]	[REDACTED]	[REDACTED]	[REDACTED]
			[REDACTED]	[REDACTED]
[REDACTED]	[REDACTED]	[REDACTED]	[REDACTED]	[REDACTED]
			[REDACTED]	[REDACTED]
[REDACTED]	[REDACTED]	[REDACTED]	[REDACTED]	[REDACTED]
			[REDACTED]	[REDACTED]

[illegible]

[REDACTED]

## 6 STATISTICAL METHODS

### 6.1 Sample Size Justification

Given the exploratory nature of this study, no formal sample size calculation was made, and no formal hypothesis testing will be performed. A total of 48 participants (16 per treatment arm) are planned to be randomized, which is considered sufficient to respond to the primary objective.

### 6.2 General Statistical Methods

#### 6.2.1 General Methods

All outputs will be incorporated into Word files, sorted and labeled according to the International Conference on Harmonization (ICH) recommendations, and formatted to the appropriate page size(s).

Tabulations will be produced for appropriate demographic, baseline, safety, efficacy, PK and PD parameters, immunogenicity, complement factors and cytokines parameters.

For efficacy and safety tables by analysis visit (or analysis visit/timepoint), only analysis visits (or analysis/timepoint) with at least 15 participants (overall) will be shown.

In the outputs, results will be presented first by cohort and then by total placebo (combined placebo from cohort 1 and 2). For general characteristics, a total column will be added as the last column. Listings will be sorted by treatment arm and participant identifier. For Immunogenicity, results will be presented by active treatment for each cohort, Total active treatment group and Total Placebo. A total column may also be added (6.6.3).

For continuous variables, full descriptive statistics will only be presented if there are at least 2 non missing observations. Alternatively, only the number of non missing data points and mean will be shown.

For categorical variables, summary tabulations of the number and percentage within each category (with a category for missing data) of the parameter will be presented.

For continuous variables except for PK, PD and immunogenicity (described below), summary tabulations will be summarized using the following standard descriptive summary statistics: number of observations, number of missing observations, arithmetic mean, standard deviation, minimum, lower quartile, median, upper quartile, and maximum. In addition, for efficacy measures, the SE and 95% CI will be provided.

Descriptive statistics for PD serum concentrations will include the number of non missing data points, the arithmetic mean, the SD, the SE, the 95% CI, the median, minimum, Q1, Q3, and maximum.

Descriptive statistics for PK serum concentrations [REDACTED] will include the number of observed values, arithmetic mean, SD, median, minimum and maximum, CV%, the geometric mean

(GM), and geometric CV% where  $\text{geometric CV\%} = \text{SQRT}(\exp(s^2) - 1) * 100$  and  $s$  is the standard deviation of the log-transformed values. Serum concentrations will be reported as received by the bioanalytical laboratory.

Descriptive statistics for immunogenicity titer values will include the number of observed values, arithmetic mean, SE, 95% CI, median, Q1, Q3, minimum, maximum, the GM, and geometric CV%.

Mean, 95% CI, Q1, Q3, and median will be presented with one more decimal place than the measured values. SE and SD will be presented with 2 more decimal places than the measured values. Minimum and maximum will be presented with the same number of decimal places as the measured values.

For event-type safety data, the number and percentage of participants with an event will be shown. The denominator will be all participants in the analysis set per treatment arm.

For cross-tabulations, the denominator will be the number of participants in the analysis set per treatment arm. For tables where results are shown by analysis visit, the denominator will be the number of participants in the analysis set per treatment arm and analysis visit. Missing values will not be included in the denominator count when computing percentages. Percentages will be presented with 1 decimal place.

If a participant is re-screened, only data from the last screening will be displayed.

Data from the SFU period will be listed only.

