### 6.6.3 Immunogenicity Evaluation

Blood samples will be collected for the determination of ADA to ARGX-117 (in serum samples) at the time points indicated in the schedule of activities (appendix 9.1).

Immunogenicity samples are analyzed in a 3-tiered approach:

- All samples are evaluated in the ARGX-117 ADA screening assay and are scored screening positive or negative
- If a sample scored screening positive, it is further evaluated in the confirmatory assay and is scored confirmed positive (positive immuno-depletion) or confirmed negative (negative immuno-depletion).
- If a sample is scored as confirmed positive, the samples are further characterized in the titration assay (to determine titer).

[figure not shown]
If available, a titer result will be reported for the ADA confirmed positive samples. However, a titer result is not always available:

- In case the ADA confirmed positive sample could not be run in the titration assay (eg, due to insufficient sample volume/quality to perform the titer analysis), the result will be described as 'positive immuno-depletion' and the sample should be considered as ADA positive.
- If a sample is negative in the titration assay, it will be reported as 'negative titer' but it should be considered as ADA positive since it was confirmed positive in the second tier.
- If a sample could not be analyzed or reported as 'positive screen', the ADA sample status is ADA unevaluable.

An overview of this 3-tiered approach and all possible sample results that will be reported by the laboratory is given below (

Figure 3). From these reported ARGX-117 ADA sample results, a final sample status should be derived during the statistical analysis, as presented in the final column ('Final Outcome'):

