**Table 17 Participant Classification for ADA Against ARGX-117**

	Highest c post baseline sample status				
Baseline ADA sample status	ADA negative	ADA positive (missing titer a )	ADA Positive (negative titer b or numerical titer value)		ADA Unevaluable
ADA negative	ADA negative	Treatment-induced ADA	Treatment-induced ADA		ADA Unevaluable
ADA positive (missing titer a )	Treatment-Unaffected ADA	ADA Unevaluable	ADA Unevaluable		ADA Unevaluable
ADA Positive (negative titer b or numerical titer value)	Treatment-Unaffected ADA	ADA Unevaluable	titer < 4 x baseline titer: Treatment-Unaffected ADA	titer ≥ 4x baseline titer: Treatment-Boosted ADA	ADA Unevaluable
ADA Unevaluable	ADA Unevaluable	ADA Unevaluable	ADA Unevaluable		ADA Unevaluable

a Samples with missing titer have as reported ADA result ‘positive immuno-depletion’ or ‘positive titer’;

b Results reported as ‘negative titer’, ie, titer value < 100 will be set to 100

c Highest sample status, with order: (from low to high) : ADA unevaluable, ADA negative, ADA positive (missing titer /positive immuno-depletion), ADA positive with titer<100 (‘negative titer’) as reported ADA result, titer value set to 100), ADA positive with titer≥100 (ie, numerical value selecting the sample with highest titer)

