**ADA unevaluable participant = participant classified as ADA unevaluable according to**

Table 17 or with missing baseline ADA sample or without postbaseline ADA samples

Note: Fourfold difference in titer values is considered significant in case a twofold serial dilution is applied (= 2 times the dilution factor) (reference to Shankar et al., 2014).

The ADA incidence is defined as the percentage of participants with treatment-induced ADAs or treatment-boosted ADAs among the number of evaluable participants.

The ADA prevalence is defined as the percentage of participants with ‘treatment-unaaffected ADA’, ‘treatment-induced ADA’ or ‘treatment-boosted ADA’ among the number of evaluable participants.

ADA analysis will be performed in the SAF set, combining data from DBTP and safety FU.

Frequency tabulations (Number and percentages) will be provided with ADA negative/positive/unevaluable samples per analysis visit and per ADA against ARGX-117 participant classification for each following treatment groups:

- ARGX-117 Dose Regimen 1
- ARGX-117 Dose Regimen 2 [REDACTED] if applicable
- ARGX-117 Dose Regimen 3 [REDACTED] if applicable
- Total ARGX-117
- Total Placebo

Frequency tabulations (Number and percentages) will be provided by treatment group and ARGX-117 combined on:

- Participants per ADA participant classification
- Prevalence and incidence of ADA
- ADA unevaluable participants
- ADA baseline positive / negative / unevaluable samples

ADA titer values against ARGX-117 will be summarized using descriptive statistics by ADA participant classification.

All immunogenicity data will be listed.

Correlation tables by ADA participant classification against ARGX-117 will be provided for the following parameters:

- Serum ARGX-117 concentration over time
- Concentration of free C2
- Percent change from baseline in free C2
- Concentration of total C2
- Percent change from baseline in total C2
- Concentration of CH50
- Percent change from baseline in CH50

- Overall Treatment-Emergent Adverse Events by MedDRA System Organ Class and Preferred Term by Overall Antidrug Antibodies Participant Classification (All Patients)
- Overall Serious Treatment-Emergent Adverse Events by MedDRA System Organ Class and Preferred Term by Overall Antidrug Antibodies Participant Classification (All Patients)
- Overall Treatment-Emergent Hypersensitivity reaction(as defined in the 6.4.1 section) by Overall Antidrug Antibodies Participant Classification (All Patients)

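### The only 95% CI listed for ADA titres appears to belong to the arithmetic mean; it should be given for the geometric mean

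*SAP*

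**What the plan says.** SAP section 6.2.1 (General Methods) fixes the titre summary in one list. It begins "Descriptive statistics for immunogenicity titer values will include the number of observed values, arithmetic mean, SE, 95% CI, median", goes on to the quartiles, and ends "minimum, maximum, the GM, and geometric CV"%. The display rule that follows groups the interval with the mean: "Mean, 95% CI, Q1, Q3, and median will be presented with one more decimal place than the measured values". No interval is listed for the GM, and no CI formula is given.

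Section 6.6.3 describes how titres arise and are used:

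- Titres exist only for some samples: "a titer result will be reported for the ADA confirmed positive samples", where available.
- They are tabulated in subsets: "ADA titer values against ARGX-117 will be summarized using descriptive statistics by ADA participant classification". The title of Table 14.2.4.3 in the list of outputs adds a breakdown by visit.
- Table 17 classes an ADA response as boosted by the ratio of the titre to baseline, with a cut-off of four. The supporting note reads "Fourfold difference in titer values is considered significant in case a twofold serial dilution is applied".
- A footnote to Table 17 on negative titres sets a floor: "titer value < 100 will be set to 100".

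Section 6.2.1 also says that "full descriptive statistics will only be presented if there are at least 2 non missing observations". Its rule of at least 15 participants per visit is worded for efficacy and safety tables, so it does not clearly remove small immunogenicity cells.

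**The concern.** The plan treats titres as multiplicative wherever it interprets them: a fold-change rule for boosting, a GM and a geometric CV%. The one measure of precision it lists nevertheless sits beside the arithmetic mean. A t-interval on the raw scale is symmetric. With a few right-skewed values it tends to be too low on the upper side, and its lower limit can drop below zero, which no titre can do.

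Titres come only from confirmed-positive samples and are split by classification and visit, within arms planned at 16 participants (section 6.1). Many cells will therefore be small. At stake is whether the error bars printed in the titre table mean what their label says.

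**Working it through.** **No figure to reproduce.** The SAP states no coverage, precision or sample size for titres.

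**Which mean the CI belongs to.** Section 6.2.1 has three comparable lists.

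| List | Arithmetic mean | SE and 95% CI | GM and geometric CV% |
|---|---|---|---|
| PD | yes | yes, after the mean | no |
| PK | yes | no | yes |
| Titres | yes | yes, after the mean | yes, at the end |

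In the PD list the CI can only be for the arithmetic mean. The titre list has the same order, with the geometric statistics added at the end. The arithmetic mean is thus the natural reading, though the SAP never says so.

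**Formulas** (assumed, as the SAP gives none), with t the 97.5% point on n − 1 degrees of freedom:

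- Raw scale: mean ± t × s/√n
- Log scale: exp(mean of ln titre ± t × s_ln/√n)

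**Worked cell, titres 100, 200, 400, 800** (n = 4, t = 3.182):

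- Raw: mean 375, s = 309.6, SE = 309.6/2 = 154.8, half-width 3.182 × 154.8 = 492.6. The CI is −118 to 868.
- Log: GM = 282.8, s_ln = 0.895, SE = 0.447, half-width 3.182 × 0.447 = 1.424, factor exp(1.424) = 4.15. The CI is 282.8/4.15 = 68 to 282.8 × 4.15 = 1,175.

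Other illustrative cells, by the same formulas:

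| Titres | Mean (95% CI) | GM (95% CI) |
|---|---|---|
| 100, 200, 400, 800, 6400 | 1,580 (−1,782 to 4,942) | 528 (73 to 3,828) |
| 100, 100, 200, 200, 400, 400, 800, 1600 | 475 (49 to 901) | 308 (136 to 697) |
| 100, 200 | 150 (−485 to 785) | 141 (1.7 to 11,561) |

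**Simulation.** Every input here is an assumption: titre = 100 × 2^k, where k is a normal variable with mean 2 rounded down and set to 0 if negative, with 40,000 samples per scenario. The two-fold steps and the floor of 100 follow section 6.6.3. The spread and n do not come from the SAP. Each entry gives raw-scale coverage / share of samples with a negative raw-scale lower limit, in %.

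| log2 SD | n = 4 | n = 6 | n = 8 | n = 12 |
|---|---|---|---|---|
| 0.5 | 89 / 5 | 97 / 0 | 94 / 0 | 95 / 0 |
| 1.0 | 92 / 42 | 92 / 10 | 85 / 3 | 89 / 0.4 |
| 1.5 | 79 / 68 | 82 / 37 | 81 / 21 | 82 / 8 |
| 2.0 | 77 / 80 | 68 / 59 | 76 / 44 | 74 / 25 |
| 2.5 | 61 / 86 | 58 / 72 | 64 / 62 | 65 / 44 |

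For SD 1.5 to 2.5, the log-scale interval covers the GM in about 92% to 94% of samples at these n. At n = 2 it covers only about 54% to 80% over the whole SD range, partly because tied titres give an interval of zero width. At n = 3 ties still matter when the spread is small, and t = 4.30 makes the interval very wide. With a wide spread and n = 4, its lower limit is below 100 in about 74% to 86% of samples.

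**The case against.** Several points against the concern stand.

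- **The link is inferred.** The list is flat and never names the mean that the CI belongs to. A reader might infer that the SAP prescribes a wrong interval outright. The text supports only the natural reading.
- **Scale and floor are less firm than they look.** The two-fold dilution is worded conditionally, and the floor of 100 appears in footnotes to the classification table. The SAP does not say that it applies to the titre summary.
- **Titres can still be compared.** A reader might conclude that titre levels could not be compared across regimens or with placebo. That does not follow, because the GM, geometric CV%, median, quartiles and range are all reported. The log-scale interval can even be rebuilt from them: with the geometric CV formula that section 6.2.1 gives for PK, s_ln = √ln(1 + CV²). For the four-titre cell the geometric CV is 110.8%, so s_ln = √ln(1 + 1.108²) = 0.895, as above.
- **Nothing depends on the interval.** The immunogenicity endpoint in section 3.2 is ADA incidence and prevalence. Boosting is judged within each participant, and no formal testing is planned.
- **The size rests on assumptions.** With a log2 SD of 0.5 to 1, raw-scale coverage is 85% to 97%, and negative limits occur in at most 3% of samples from n = 8.

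These points limit the consequence. They do not give a reason to keep the raw-scale interval as the only one. If the GM was meant, the sentence still needs to say so.

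**Conclusion.** The point holds as a minor one. On its natural reading, section 6.2.1 puts the only titre interval on the raw scale, although the plan otherwise treats titres by fold change. Over log2 SD 0.5 to 2.5 and n = 4 to 12, coverage would be about 58% to 97%, with a negative lower limit in 0% to 86% of samples. The poor end needs wide spread, and negative limits are most frequent in the smallest cells. The SAP fixes neither spread nor cell size, so a firm claim of coverage far below 95%, or of routinely negative limits, is not supported. The effect is confined to one descriptive row.

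**What to change.** In section 6.2.1:

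- State that the 95% CI for titres is for the geometric mean, computed as a t-interval on log titres and back-transformed.
- Drop the SE and 95% CI of the arithmetic mean for titres. Keep the arithmetic mean, median, quartiles and range as descriptive values.
- Show no CI in very small cells such as n = 2 or 3, where neither interval is reliable.

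The cost is one amended sentence and a small programming change, since log titres are already needed for the GM and geometric CV%. There is a small downside. Some very small cells will show no interval, and elsewhere the lower limit may still fall below 100, as in the five-titre example (73), though never below zero.

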#### 6.2.1.1 eCOA data

The following efficacy assessments are reported using an electronic clinical outcome assessment (eCOA) platform or web portal: mMRC, GS, MMN-RODS, 9-HPT, EQ-5D-5L, CAP-PRI, PGIC, FSS, HRPQ, TSQM-14. In addition, C-SSRS and PHQ-9 are also assessed with the eCOA platform.

The Appendix 9.3 presents the derived variables directly computed by the eCOA platform. Some variables will be re-derived and used for the statistical analysis.

#### 6.2.1.2 Efficacy analyses

For efficacy endpoints, descriptive summary tables will present the analysis visits and the 2 following last assessment derived visits:

- last assessment analysis visit during DBTP, defined as the last non missing post baseline value in the DBTP including the unscheduled visits
- last assessment before first IVIg retreatment analysis visit, defined as the last non missing post baseline value in the DBTP including the unscheduled visit, before the participant has been retreated with IVIg. Efficacy assessments performed on the day of retreatment of IVIg should be considered. In the case the participant has not been retreated with IVIg, last assessment available during the treatment period will be used.

These 2 derived visits are applicable for mMRC, MMN-RODS, 9-HPT, EQ-5D-5L, CAP-PRI, PGIC, FSS, HRPQ and TSQM-14. For HRPQ, the last available questionnaire with at least one non missing answer for all items from HRPQ01 to HRPQ09 (based on SDTM datasets) will be used.

For daily data for GS, descriptive summary tables will present the 3 following assessments:

- last assessment analysis visit during IVMP, defined as the last non missing post-IVMP baseline value, in the IVMP period including the unscheduled visits
- last assessment during DBTP, defined as the last non missing post baseline value during DBTP
- last assessment before first IVIg retreatment, defined as the last non missing post baseline value in the treatment period before the participant has been retreated with IVIg. Efficacy assessments performed on the day of retreatment of IVIg should be considered. In the case the participant has not been retreated with IVIg, last assessment available during the treatment period will be used.

Given the exploratory nature of the trial, there will be no formal hypothesis testing. Summary statistics, as well as 95% CIs on selected parameters, will be presented as described in the sections below.

For the analysis of continuous endpoints (including mMRC, MMN-RODS, CAP-PRI and GS), each ARGX-117 treatment group will be compared to the placebo group of the respective cohort.

[REDACTED]

■ [REDACTED]

[REDACTED]

[REDACTED]

[REDACTED]

[REDACTED]

[REDACTED]

[REDACTED]

[REDACTED]

[REDACTED]

■ [REDACTED]

[REDACTED]

[REDACTED]

[REDACTED]

[REDACTED]

[REDACTED]

[REDACTED]

For efficacy endpoints, exploratory analyses could be performed considering the longitudinal aspect of the data.

